1.0 Objectives

1.1 Study Objectives

Aim: To determine the effect on food and energy intake of varying the proportion of lower-energy-dense vegetables and fruits in meals served over five days to preschool children.

Hypotheses:

1. When low-energy-dense vegetables and fruits are added to children's meals over five days (Addition condition):
 - a. Daily energy intake will increase compared to the Baseline condition
 - b. Daily vegetable and fruit intake will increase compared to the Baseline condition
 - c. Daily food and beverage intake will increase compared to the Baseline condition
 - d. Daily food energy density will decrease compared to the Baseline condition
2. When low-energy-dense vegetables and fruits are substituted for foods higher in energy density in children's meals over five days (Substitution condition):
 - a. Daily energy intake will
 - i. decrease compared to the Baseline condition
 - ii. decrease compared to the Addition condition
 - b. Daily vegetable and fruit intake will
 - i. increase compared to the Baseline condition
 - ii. increase compared to the Addition condition
 - c. Daily food and beverage intake will
 - i. not differ significantly from the Baseline condition
 - ii. decrease compared to the Addition condition
 - d. Daily food energy density will
 - i. decrease compared to the Baseline condition
 - ii. decrease compared to the Addition condition
3. Across all three conditions of different proportions of low-energy-dense vegetables and fruits, daily intakes of vegetables, fruit, and energy will begin to converge over the five-day period

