6.2 Study Procedures

1. Over five consecutive days, enrolled children will be served breakfast, lunch, dinner, and snacks of foods commonly served in the childcare center following their regular meal and snack schedules - menus were developed from the menus at the childcare centers to be as similar as possible to the foods that children are regularly served. Milk or water will be served as beverages. Meals will be served at tables of three to six children and one adult, which is a standard practice at the childcare centers. The adults at the table will be instructed not to discuss the food or to encourage the children to eat. There will be three conditions, with changes only in the proportion of lower-energy-dense vegetables and fruits at the meals. Each participant will be served an individual pre-weighed meal. All food and beverage items will be weighed with a food scale before and after meals and snacks to within 1 gram in order to determine the amount consumed. Participants will be told they can eat as much or as little of the foods as they would like. Trained observers (research personnel) will document food and beverage spillage and any comments made about the food. The children will be provided with an evening snack pre-packaged for consumption at home. Any leftover food from the evening snack will be returned to the childcare center the following day to be weighed.
2. In the event of extenuating circumstances (e.g. unexpected childcare center closure, inclement weather) the researchers may decide to pack out a meal, or meals, which can be consumed outside of the childcare center. Participants will be notified in advance if this should occur. Any leftover food from a packed meal, or meals, will be returned to the childcare center the following day to be weighed. Applicable instructions for serving or reheating will be provided.
3. Parents will be asked not to serve any additional food or beverages to their child apart from those provided by the study and water. If the participant deviates from the procedure and consumes extra food, the estimated food and beverage consumption will be requested.

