4. Physical activity levels will be measured over the five consecutive days using triaxial accelerometers. The accelerometers will be worn while the children are present at the childcare center (from before breakfast to after dinner). Research staff will attach a device to the child's waist upon arrival at the center each morning and remove the device upon the child's departure from the center each evening.
5. On the 16th visit to the childcare center, children will have their height and weight measured by a trained staff member of the lab. Body weight will be measured in triplicate using a portable digital scale. Height will be measured in triplicate using a portable stadiometer. The children will also complete the Tasting Game. They will be given small samples of foods served in the study and asked to point to a cartoon face that represents their liking of the food on a scale of yucky to

yummy. Children will also look at three plates (one from each condition) from two meals and be asked which they would prefer.

6. Parents will be asked to complete an Evening Report Form, Background Questionnaire, the Children's Eating Behavior Questionnaire, the Caregiver's Feeding Style Questionnaire, and the Child Feeding Questionnaire. The Evening Report Form will be completed at the end of each study day and returned each morning to research personnel. All questionnaires (the Background Questionnaire, Children's Eating Behavior Questionnaire, Caregiver's Feeding Style Questionnaire and Child Feeding Questionnaire) will be administered during the last five days of the study. All questionnaires will be completed via pencil and paper.
7. Photos of children eating, participating in the tasting game, and having their height and weight measured may be taken.
8. There will be a minimum of a one-week break between study weeks. There will be a four- to six-week wash-out period between running this and any previous experiments at each childcare center.
9. Approved lab staff (on this IRB application) will email parents the Friday before a study week to remind parents of the start of the study.

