6.3 Duration of Participation

The duration of the study will be five consecutive days, and each participant will be asked to complete three of these five-day periods. Within each day, each meal and snack will take approximately 30 minutes to complete. The estimated time required by the participant each day is 2.5 hrs. The estimated total time required for all of the meals is 37.5 hours. The height and weight measurements and the Tasting Game on the final visit after the 15 days are completed will require an additional hour of time. For the parents, another 30 minutes will be requested to complete the questionnaires. The total time commitment for the study is 39 hours. Teachers will spend approximately 20 minutes per questionnaire.

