7.2 Statistical methods

The study hypotheses will be assessed using linear mixed models with repeated measures. Differences in mean outcomes will be tested across the three experimental conditions of the proportion of vegetables and fruits served in meals, as well as across the five days of intake.

Hypotheses 1 and 2 test whether variations in the proportion of low- and high-energy-dense foods influence the mean daily outcomes of energy intake, food and beverage intake, and energy density. To test these hypotheses, the fixed factors in the models will be condition, study week, study day, menu, childcare center, classroom, and sex. Interactions between these factors will be tested and removed from the model if not significant and participants will be treated as a random effect. The Tukey-Kramer method will be used to adjust for multiple pairwise comparisons between means. The energy content of parentally reported non-study food consumption will be estimated by research staff. Daily energy intake will be analyzed both with and without the non-study items.

Hypothesis 3, concerning whether daily energy intake in the three conditions converges over each five-day period, tests whether regulation of energy intake occurs over time in response to variations in the proportion of low- and high-energy-dense foods served. To test this hypothesis, a random coefficients model will be used. The trajectories of intake over time will be allowed to vary randomly across subjects; thus, they will be modeled separately for each child. Time (study day) will be treated as a continuous covariate in the model and polynomial factors of time (linear and quadratic coefficients) will be tested as both fixed and random effects to determine the shape of the intake trajectory. The intercept of the trajectory will reflect the magnitude of daily intake at Day 1

and the linear coefficient will represent the rate of change in intake (slope) across time after Day 1. The quadratic coefficient, if significant, will represent the rate of acceleration or deceleration in intake (curvature) across time after Day 1.

It has been predetermined that children who have incomplete intake measures on ≥ 3 days in all 3 conditions will be excluded from analysis. It has also been predetermined that children who eat $>95\%$ of the food weight served on at least 1 day will be classified as “plate cleaners”, and their influence on the results will be tested.

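### Does the unstated return of Day 5 home leftovers and forms, with no rule for incomplete days, undermine the Hypothesis 3 convergence test?

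*Combined protocol and SAP*

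**What the plan says.** The evening snack is eaten at home. Section 6.2 says of it: "Any leftover food from the evening snack will be returned to the childcare center the following day to be weighed". The daily parent form follows the same pattern: "The Evening Report Form will be completed at the end of each study day and returned each morning to research personnel". The reminder section of 6.2 has staff who "will email parents the Friday before a study week to remind parents of the start of the study".

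Meals occupy 15 days in three five-day periods. One further visit is described: "On the 16th visit to the childcare center, children will have their height and weight measured by a trained staff member of the lab", which section 6.3 places "on the final visit after the 15 days are completed". No visit is described after Day 5 of weeks 1 and 2.

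Hypothesis 3 in section 1.1 expects that "daily intakes of vegetables, fruit, and energy will begin to converge over the five-day period". Section 7.2 tests this with a random coefficients model: "Time (study day) will be treated as a continuous covariate in the model", with linear and quadratic terms. Its only rule for incomplete data is that "children who have incomplete intake measures on ≥ 3 days in all 3 conditions will be excluded from analysis". Separately, section 3.3.1 removes children who miss too many days or meals within one study week.

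**The concern.** A reminder sent on a Friday before five consecutive days at a childcare center suggests a Monday-to-Friday week. The day after Day 5 would then be a Saturday, and next-day return would fail on the same day in every period. The exclusion rule in 7.2 would not respond, because it acts on children and needs at least three incomplete days per condition. Analysts would be left to choose between a missing day, a partial total and a snack counted as fully eaten.

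The stake is Hypothesis 3. Days 1 and 5 are the ends of the trajectory and carry the most weight in a linear slope. If children compensate at home in the evening, a lost Day 5 snack or report could hide it. A mixed model tolerates sporadic missing days, but it cannot recover an end day that is always absent, and it does not correct one kept as a partial total.

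**Working it through.** **1. Is collection impossible?** The documents give neither the weekdays of a study week nor the center's weekend hours. Monday to Friday is a fair inference; Saturday closure is an assumption. Section 3.1 requires children to be enrolled at the center, so a container and a paper form can come back on the next center day, within the break between study weeks. After week 3 there is also the 16th visit, whose date is not given. Day 5 return is therefore unspecified, not ruled out.

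**2. Does the 7.2 exclusion respond to Day 5 losses?** One lost Day 5 per period gives 1 incomplete day per condition, against a threshold of 3. In total that is 3 of 15 days (20%). No child would be excluded on this ground, and the analysed number is not affected.

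**3. Precision, worst case (every Day 5 missing).**
- Sum of squares of day about its mean, Days 1-5: 4 + 1 + 0 + 1 + 4 = 10. Days 1-4: 2.25 + 0.25 + 0.25 + 2.25 = 5.
- Variance ratio for the slope, and for a slope difference between two conditions: 10/5 = 2.00; SE × √2 = 1.41.
- Share of squared slope weight: 0.2²/(0.2² + 0.1² + 0 + 0.1² + 0.2²) = 0.04/0.10 = 40% for Day 5, and the same 40% for Day 1.
- Starting from an assumed 90% power (two-sided 5%; 1.960 + 1.282 = 3.242): Φ(3.242/1.414 − 1.960) = Φ(0.33) = 63%.
- If slopes also vary by condition within child, with variance s relative to the residual, the ratio is (1/5 + s)/(1/10 + s). For assumed s = 0.05, 0.1 and 0.2 this gives 1.67, 1.50 and 1.33, with power 71%, 75% and 80%.
- If Day 5 is recovered in week 3 only, power is 75% to 84% under the same range of assumptions.
- Curvature term: contrast sum of squares 14 on five days and 4 on four, so variance × 14/4 = 3.5. In the quadratic model with the intercept at Day 1, Day 5 holds 11% of the squared weight of the linear term and Day 1 holds 48%.

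The 90% is illustrative. Section 7.1 attaches it to a 50 kcal difference between Baseline and Substitution, not clearly to a slope contrast. The 48 in 7.1 cannot be reproduced because no SD is given; solving backwards for a paired contrast gives 50 × √48/3.242 ≈ 107 kcal. Nothing here depends on that figure.

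**4. Bias, if Day 5 is kept as a partial total.**
- Slope weight of Day 5: (5 − 3)/10 = 0.2. A shortfall of m kcal shifts a condition's slope by −0.2m kcal/day.
- Snack energy is not in the documents. Section 7.1 implies about 50/0.05 = 1,000 kcal/day. Assuming the snack is 5% to 20% of this (50 to 200 kcal), the overall slope shifts by −10 to −40 kcal/day if all are lost, or −2.5 to −10 if a quarter are.
- Hypothesis 3 concerns the difference between condition slopes: −0.2m − (−0.2m) = 0 when the shortfall is equal.
- If the shortfall differs by an assumed 25 kcal: 0.2 × 25 = 5 kcal/day with every Day 5 lost, and 5 × 0.25 = 1.25 kcal/day with a quarter lost.

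**5. Hypotheses 1 and 2.** The same assumed 25 kcal difference moves a five-day mean contrast by 25/5 = 5 kcal, against the 50 kcal that 7.1 treats as meaningful. An equal shortfall moves it by zero.

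**6. The parent form.** It supplies non-study food only. Section 7.2 already plans the energy analysis with and without those items, and the second does not need the form.

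**The case for a change.** The strongest case for a change needs no assumption about weekdays. Section 7.2 has no day-level rule at all. Section 6.2 also allows packed meals to be eaten outside the center and returned the next day, so incomplete days are foreseeable on any study day. Without a stated rule, the choice would be made after data are seen, on a day that may be an end of the trajectory, and a few sentences would settle it.

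The silence is real, and so is the influence of Day 5 on a linear slope. But a next-center-day return and a working definition of an incomplete day are details that field staff and analysts supply as a matter of course. The steps beyond that are not clear gains. Setting a whole day to missing for one unweighed item would discard meals weighed at the center and, if Day 5 items stayed uncollected, would itself produce the precision loss in step 3. A center-only model keeps Day 5 but omits home eating, which is where evening compensation would appear. Leftovers returned on a Monday would be three nights old. These are arguable trade-offs, and none is shown to correct a wrong result.

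**Conclusion.** No change to the plan follows. Sections 6.2 and 7.2 leave two details unstated: when Day 5 home items come back after weeks 1 and 2, and how an incomplete day enters the analysis. Neither omission makes the data uncollectable or the convergence test invalid.

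The upper bound on harm is a doubled slope variance (63% power from an assumed 90%). It depends on a Friday Day 5, a closed center, no later return, and every Day 5 then set to missing. The documents state none of these. The bias relevant to Hypothesis 3 is zero for a shortfall common to all conditions, and 5 kcal/day under the assumed 25 kcal difference with complete loss. The overall-slope shifts of −10 to −40 kcal/day concern a quantity that no hypothesis tests. Hypotheses 1 and 2 are little affected.

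The conclusion would weaken if Day 5 items were in fact never collected and home evening intake differed materially by condition; the documents give no sign of the first and no figure for the second.

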8.0 Confidentiality, Privacy and Data Management

8.1 Confidentiality

We will take photos of the children having a test meal and may use them for poster or oral presentations at scientific meetings. Parents will check on their consent form if they agree to have their child's photo taken. All images will be stored on a password-protected network drive that only those on this application have access to. Images will be stored with a generic title and will not be labeled with any identifiable information. The images will be deleted from the drive within three years of completion of the study.

8.1.1 Identifiers associated with data and/or specimens

Subjects will only be identified by a three-digit subject number, dot color, and a letter of the alphabet.

Teachers will not have their own identifiers.

8.1.1.1 Use of Codes, Master List

The master list that links subject numbers to personal information will be stored in a locked closet in the Lab Manager's office. Only those listed on this application will have access to it. The master list will be destroyed upon

publication of the study or five years after the close of the study, whichever comes first.

8.1.2 Storage of Data and/or Specimens

Paper data will be stored in a locked cabinet in a locked closet in the Lab Manager's office. Data on network drives will have no identifiable information. All computers and network drives are password protected.

Paper and computer records of data will be stored indefinitely with identifiers removed. Paper records will be stored in a locked filing cabinet in the Lab Manager's office. Computer records will be stored on a password-protected network drive that only those on this application have access to.

This study will be issued a Certificate of Confidentiality. Researchers will not disclose or provide any identifiable information without the subject's prior consent or where permitted according to NIH's Policy on Issuing Certificates of Confidentiality.

8.1.3 Access to Data and/or Specimens

Only those listed on this application will have access to the data.

8.1.4 Transferring Data and/or Specimens

The researchers do not plan to release identifiable information collected in the study. However, if researchers consider releasing identifiable information in the future – the individual or institution receiving the identifiable information will be made aware they are also subject to the requirements of subsection 301(d) of the Public Health Service Act.

8.2 Privacy

No personal information other than first name of the child, and telephone number and email address of the parent, is accessible to research staff. Subjects remain anonymous except for study number and letter. Only senior staff members listed on this IRB application will have access to personal information such as address, age, weight.

Data on food consumption is collected in a separate room where only study staff is present. Heights and weights for children are collected in a private area of the child's classroom.

9.0 Data and Safety Monitoring Plan

The proposed study poses minimal risk to participants, since the procedures involve little change from the usual meals and activities at the childcare centers.

10.0 Risks

There are minimal risks associated with participation in this project. The risks are no greater than those associated with the children's usual attendance and consumption of meals at the childcare center and at home, which include the risk of food allergy, food-borne illness, and choking on food.

The amounts of food and beverages served in all conditions meet or exceed minimum requirements for calorie and nutrient content for this age group as specified by the USDA and CACFP.

There are no potential risks for teacher participants.

11.0 Potential Benefits to Subjects and Others

11.1 Potential Benefits to Subjects

There are no direct initial benefits to subjects participating in the proposed study.

11.2 Potential Benefits to Others

The research will benefit society by advancing understanding of children's eating behavior and identifying meal-related strategies for the prevention of obesity in children.

12.0 Sharing Results with Subjects

No results will be shared with the subjects.

13.0 Economic Burden to Subjects

13.1 Costs

N/A

13.2 Compensation for research-related injury

It is the policy of the institution to provide neither financial compensation nor free medical treatment for research-related injury. In the event of injury resulting from this research, medical treatment is available but will be provided at the usual charge. Costs for the treatment of research-related injuries will be charged to subjects or their insurance carriers.

14.0 Other Approvals

Local childcare centers have given permission for the conduct of this research in their facilities. Letters of permissions are on file with the Institutional Review Board.

15.0 Adverse Event Reporting

15.1 Reporting Adverse Reactions and Unanticipated Problems to the Responsible IRB

In accordance with applicable policies of The Pennsylvania State University Institutional Review Board (IRB), the investigator will report, to the IRB, any observed or reported harm (adverse event) experienced by a subject or other individual, which in the opinion of the investigator is determined to be (1) unexpected; and (2) probably related to the research procedures. Harms (adverse events) will be submitted to the IRB in accordance with the IRB policies and procedures.

15.2 Auditing and Inspecting

The investigator will permit study-related monitoring, audits, and inspections by the Penn State quality assurance program office(s), IRB, the sponsor, and government regulatory bodies, of all study related documents (e.g. source documents, regulatory documents, data collection instruments, study data). The investigator will ensure the capability for inspections of applicable study-related facilities (e.g. pharmacy, diagnostic laboratory).

16.0 Study Monitoring, Auditing and Inspecting

16.1 Auditing and Inspecting

The investigator will permit study-related monitoring, audits, and inspections by the Penn State quality assurance program office(s), IRB,

the sponsor, and government regulatory bodies, of all study related documents (e.g. source documents, regulatory documents, data collection instruments, study data). The investigator will ensure the capability for inspections of applicable study-related facilities (e.g. pharmacy, diagnostic laboratory).

